**Phase 2 Specific Aim:**

Baseline and post 6 weeks of chokeberry:

All statistical analyses associated with this cross-sectional portion of the study will be performed using a statistical analysis system software (SAS v9.4, Carry, NC). To investigate the association between the cross-sectional measures (i.e., adverse childhood experiences, historical trauma, resiliency, presence of anxiety and depression, metabolic markers (i.e., 8-OHdG, IL-6, lipids, glucose, CRP, blood pressure)) and baseline epigenetic measures, simple and multivariable linear regression models will be run. Adjustment will be made for the confounders of interest (i.e., smoking status, BMI, physical activity levels, presence of comorbidities, anti-depressant and/or anti-anxiety medication use, supplement use, nutritional intake, age and gender). For the metabolic end points, the values will be expressed as means ± SD. Statistical tests will be performed using the same commercial software package (SAS v9.4, Carry, NC) as described above. The Kolmogorov–Smirnov test will be applied to determine whether the continuous variables are normally distributed. For within group comparison vs baseline, variables showing normal distributions will be evaluated using the paired t test, while variables showing non-normal distributions will be evaluated using the Wilcoxon signed rank test. Our null hypothesis is that chokeberries will not have an effect on gene expression, metabolic markers or mental health status in Great Plains Indian subjects. As noted previously, a p-value of <0.05 will be considered as

statistically significant for all statistical assessments in this research project. Again, future research steps could include a more complex mixed model design where interaction and mediation effects can be tested with a larger sample size pending the outcomes noted here. See *Figure 2*, above for a summary of the study steps.

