### **Experimental Design:**

Fifty participants will be recruited in a rolling sample collection from the Greater Grand Forks area of North Dakota and Minnesota. A respondent driven rolling sampling method will be used for adults between the ages of 18-65 years of age. Ages have been specified as such due to the substantially changing metabolic profiles in children and older adults. We have proposed a first step cross-sectional baseline data collection process followed by a longitudinal intervention design in this exploratory study examining the effects of consuming traditional Indigenous chokeberry on metabolic, epigenetic and mental health markers where subjects will serve as their own control.

*Randomization Note:* It is considered almost unethical at this time to conduct double blind, placebo control studies with Indigenous subjects. There has been long-standing historical mistrust that Indigenous communities have with research. This is due to often being taken advantage of in the past by researchers, and even having been the subject of experimental studies that would have been considered illegal by today's IRB standards. The idea of 'tricking' somebody with a placebo agent is not a way to build trust with this population, so adjustments to the standard study design are imperative to build trust, research interest and capacity in Indigenous settings. By supporting Indigenous investigators to lead research with their own populations gives further opportunity for community trust building with institutional settings. This is consistent with the NIH's own 2019-2023 Strategic Plan for Tribal Health Research which helps define the research variables and goals for research in Indigenous communities. The project has been designed with the best possible rigor that is realistic in an American Indian participant setting with involvement of the American Indian community including an Elder to ensure involvement and success.

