### **Sample Size, Power and Attrition:**

The proposed project aims to test the differences in gene expression, epigenetic (e.g. methylation) and metabolic endpoints (e.g. IL-6, 8-OHdG, lipids) between baseline and post 6 weeks of daily chokeberry consumption. Our sample will include fifty American Indian participants. With a sample of 50 and a conservative effect size as small as 0.4, we have a power of 79.2% with a two-sided paired test and level of significance at 0.05. We consulted the literature on the effects of our proposed chokeberry intervention on the metabolic outcome measures proposed in our study. The median effect size from these studies in the literature (significant findings) is 1.12, which is much higher than 0.4. Therefore, we expect to have a power higher than 79.2%. As to epigenetic endpoints, to the best of our knowledge, there is no study that has been published to

test chokeberry's effects on human IL-6 promoter CpG island methylation changes. Only a few cell culture studies have shown DNA methylation changes using anthocyanin rich fruits with reported effect size >0.4. Thus, we believe that we should have sufficient power to perform the proposed exploratory study with a sample of size 50. As American Indian populations (which are the basis for this study) have unique research needs and history, we consulted the literature to determine the average attrition rate of studies with the American Indian population. We were able to find literature specific to the reservation areas of North Dakota and used this information in our calculations.

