**Phase 1 Specific Aim:**

For this portion of the statistical analysis, an established method for analyzing epigenetic differences at time points will be utilized. It must be noted that due to the small sample size in this exploratory study design the following statistical procedures will be employed. Normality of continuous variables will be assessed. For non-normal data, appropriate transformations (e.g. log transformations) and/or non-parametric tests will be applied for further statistical analysis. Back-transformations will be used for the interpretation of the final results. Correlation analyses will be performed by the Pearson's correlation test (or Spearman correlation for non-normal data). A general linear model with repeated measurements will be used to assess differences between baseline and post 6 weeks of daily chokeberry consumption with confounding variables adjusted. If multiple epigenetic markers are tested, family-wise Type I error rate will be controlled with standard methods (e.g. Bonferroni, False Discovery Rate method). The Student's t-test for independent samples will be performed to assess gender differences. A p-value of <0.05 will be considered as statistically significant for all statistical assessments in this research project. Future research steps could include a more complex mixed model design where interaction and mediation effects can be tested with a larger sample size pending the outcomes noted here.

[figure not shown]

Figure 2. Three step research strategy

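### No methylation or expression analysis accounts for cell composition: the baseline covariate list omits it and the six-week model names no covariates, which matters if the specimen is mixed-cell

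*Combined protocol and SAP*

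**What the plan says.** The combined protocol and SAP has three analyses that bear on this point.

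- **Baseline associations (Phase 2 Specific Aim).** Trauma, mental-health and metabolic measures, including CRP and IL-6, are related to "baseline epigenetic measures, simple and multivariable linear regression models will be run". The covariates are stated: "Adjustment will be made for the confounders of interest (i.e., smoking status, BMI, physical activity levels, presence of comorbidities", continuing with "anti-depressant and/or anti-anxiety medication use, supplement use, nutritional intake, age and gender". That is four factors plus five, nine in all. The list is introduced by i.e., so it reads as complete.
- **Six-week epigenetic change (Phase 1 Specific Aim).** The text says "an established method for analyzing epigenetic differences at time points will be utilized" without naming the method. A repeated-measures linear model is to "assess differences between baseline and post 6 weeks of daily chokeberry consumption with confounding variables adjusted". No covariate is listed.
- **Within-group comparisons (Phase 2 Specific Aim).** A paired t test or Wilcoxon signed rank test is used, and neither takes covariates. They are introduced for the metabolic endpoints, but the null hypothesis that follows also covers gene expression.

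The Sample Size, Power and Attrition section names the methylation target when it notes that no published study was found to "test chokeberry's effects on human IL-6 promoter CpG island methylation changes". The design has a single arm, "where subjects will serve as their own control". The available text does not name the specimen and does not mention a differential count, cell sorting or statistical estimation of cell proportions.

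**The concern.** A methylation value from a specimen of several cell types is a weighted average of the values in those types. If the proportions move, the measured value moves even when no cell has changed. Expression measured in mixed cells has the same weakness.

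Two sets of results are exposed. At baseline, a participant with more inflammation may have a different cell mix, so an association between CRP or IL-6 and methylation could arise from the mix alone. Over six weeks, pairing removes stable personal traits but not a within-person shift in cell proportions, and there is no control arm to show what shift occurs without the berry. At stake is whether a positive finding can be described as methylation or expression changing within cells.

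**Working it through.** **1. The plan's own figure.** Inputs from the Sample Size, Power and Attrition section: n = 50, standardised effect 0.4, two-sided paired test, significance level 0.05. With the noncentral t distribution, df = 49 and noncentrality 0.4 × √50 = 2.83, power is 79.18%. This reproduces the stated 79.2%. The same function gives the chance that a spurious mean shift of a given size is declared significant.

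**2. Formula for the six-week change.** With two groups of cells, fraction p with methylation m1 and fraction 1 − p with methylation m2, the measured value is p·m1 + (1 − p)·m2. If m1 and m2 stay fixed, the change is (shift in p) × (m1 − m2). Dividing by the SD of the paired change gives the spurious standardised effect.

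**3. Inputs.** The documents give no cell fractions, no methylation difference between cell types and no SD of change. All three are assumed here, in two sets.

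| Assumed set | Shift in fraction (points) | Difference between cell types (points) | SD of change (points) | Spurious change (points) | In SD units |
|---|---|---|---|---|---|
| A | 1 to 5 | 5 to 30 | 2 to 5 | 0.05 to 1.5 | 0.01 to 0.75 |
| B | 2 to 8 | 10 to 40 | 3 to 4 | 0.2 to 3.2 | 0.05 to 1.07 |

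Ends of set A: 0.01 × 5 = 0.05 and 0.05/5 = 0.01; 0.05 × 30 = 1.5 and 1.5/2 = 0.75. Ends of set B: 0.02 × 10 = 0.2 and 0.2/4 = 0.05; 0.08 × 40 = 3.2 and 3.2/3 = 1.07.

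A middle case in set A is 0.03 × 20 = 0.6 points, and 0.6/3 = 0.2 SD. In set B, the 12 products of differences 10, 20, 30, 40 and shifts 0.02, 0.05, 0.08 have a median of 0.9 points, which is 0.9/4 = 0.23 to 0.9/3 = 0.30 SD.

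**4. Chance of p < 0.05 with no within-cell change (n = 50, all completing).**

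| Spurious shift | Declared significant |
|---|---|
| 0.01 SD | 5.1% |
| 0.1 SD | 10.7% |
| 0.2 SD | 28.4% |
| 0.3 SD | 54.8% |
| 0.4 SD | 79.2% |
| 0.5 SD | 93.4% |

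**5. Baseline regressions.** Leaving out cell fraction biases the coefficient of, say, CRP by (m1 − m2) × (slope of cell fraction on CRP, given the nine covariates). The documents supply neither factor, so no figure can be given. The bias is zero only if one of them is zero.

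**The case against.** The strongest objections, and what stands of each:

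- **The nine factors are not the six-week covariates.** A reader might infer that the change model adjusts for those nine and deliberately leaves out cell composition. The documents do not support this. The list belongs to the baseline regressions, where no six-week shift can occur, and the change model simply does not say what it adjusts for. The gap remains, and carrying the list over would help little, because factors that are stable over six weeks cannot account for a within-person change.
- **The specimen is not stated.** If DNA and RNA come from one isolated cell type, the point falls away. This stands, so the point is conditional. The unnamed method, and the general allowance for model adjustments in the Statistical Design and Power of Study section, mean that adjustment for cell mix is not ruled out. They do not commit the plan to it.
- **Not every shift is bias.** Sporadic infections mainly add variance; a spurious mean change needs a shift that is systematic across participants. If the berry itself moves the cell mix, that shift is a mediator and the bulk change is truly caused by the berry. Both statements are right. They limit what adjustment can show, and they are why the unadjusted estimate must be kept.
- **The size is assumed.** With a 30-point difference, a 5-point shift and an SD of 3 to 4, the artefact is 1.5/4 = 0.38 to 1.5/3 = 0.50 SD. A reader might infer that it matches the 0.4 used for power. That case lies above the middle of its own assumed grid, and the documents do not favour it over a negligible value.
- **The study is exploratory.** True, but its results are meant to guide larger studies, and a cell count not taken at a visit may not be recoverable.

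**Conclusion.** The point holds, conditional on a mixed-cell specimen. The only covariate list in the plan omits cell composition, the six-week model names no covariates, and the paired tests use none. A single-arm before-after comparison cannot by itself separate a shift in cell mix from a within-cell change. The size is unknown: about 0.01 SD to about 1 SD across the assumed inputs, with middle cases of 0.2 to 0.3 SD. At 0.2 SD the false-positive chance is 28.4%, against a nominal 5%.

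The documents do not support saying that a positive result would be spurious, that white-cell mix will in fact shift over six weeks, or that the artefact equals the design effect. What they support is that the plan, as written, could not tell these possibilities apart.

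**What to change.** 1. State the specimen and any cell isolation step for the methylation and expression assays, and name the covariates of the six-week model in the Phase 1 Specific Aim section.
2. If the specimen is mixed-cell, obtain cell proportions at both visits, either from a differential on blood already drawn or, if an array is used, by estimation from the methylation data. The lipid, glucose and CRP measurements suggest that blood is drawn; that it is suitable for a differential at both visits is an assumption to confirm.
3. Add one or two cell fractions to the baseline model in the Phase 2 Specific Aim section.
4. Report the six-week methylation and expression change without adjustment and, as a sensitivity analysis, adjusted for the within-person change in cell fraction. Regress the change in the endpoint on the change in fraction and read the adjusted change at zero change in fraction. Centring that covariate at its sample mean would merely return the unadjusted mean.
5. If the change does not persist after adjustment, describe it as a change in the bulk specimen that may reflect cell composition. If it does persist, do not treat that as proof of a chokeberry effect, since the design has no control arm.

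**Cost.** One or two degrees of freedom. In the change analysis 49 becomes 48 or 47. In the baseline model, with one parameter for each of the nine factors, one for the exposure and an intercept, 50 − 11 = 39 becomes 38 or 37. There is a small laboratory cost for a differential, or none if an array is used. Adjustment may also remove a cell shift that the berry caused, which is why both estimates are reported.

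### Drugs that act on the metabolic endpoints are missing from the baseline confounder list and, separately, changes in them between visits are not handled in the before-after tests

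*Combined protocol and SAP*

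**What the plan says.** The Phase 2 Specific Aim describes two analyses that should be kept apart.

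- **Baseline regressions.** Cross-sectional measures, including the metabolic markers "8-OHdG, IL-6, lipids, glucose, CRP, blood pressure", are related to baseline epigenetic measures by linear regression. The stated confounders are "smoking status, BMI, physical activity levels, presence of comorbidities, anti-depressant and/or anti-anxiety medication use, supplement use, nutritional intake, age and gender". The list is introduced by i.e., so it reads as complete.
- **Before-after tests of the metabolic markers.** "For within group comparison vs baseline, variables showing normal distributions will be evaluated using the paired t test"; non-normal variables go to the Wilcoxon signed rank test. Neither test carries covariates.

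The Experimental Design section describes a single group "where subjects will serve as their own control". The power statement under Sample Size, Power and Attrition rests on the same comparison, "between baseline and post 6 weeks of daily chokeberry consumption", "with a two-sided paired test and level of significance at 0.05".

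Two other passages touch on adjustment. The Phase 1 Specific Aim adjusts a repeated-measures linear model for confounders that it does not name, in a section about epigenetic differences. Statistical Design and Power of Study allows model adjustments as needed, in connection with the checking of statistical assumptions. Neither mentions a change in medication.

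**The concern.** By listing psychotropic medicines the plan accepts that drug use can confound, yet it leaves out the classes that act directly on its own markers: lipid-lowering, glucose-lowering, blood-pressure-lowering, and anti-inflammatory or steroid drugs. This matters in different ways for the two analyses.

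In the baseline regressions, a marker value lowered by treatment is read as the participant's natural level. The comorbidity term helps only in part, because it cannot separate treated from untreated people who have the same condition.

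In the before-after tests, fixed characteristics and stable treatment largely drop out of each participant's difference. A treatment that is started, stopped or altered between the visits does not. With no concurrent arm, nothing in the planned test separates that shift from an effect of the berry. The plan's null hypothesis is that chokeberries have no effect, so a significant change will be read as a chokeberry effect. If changes in medication are not recorded by week 6, the question may be hard to settle afterwards.

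**Working it through.** **The plan's own figure.** The plan states: "With a sample of 50 and a conservative effect size as small as 0.4, we have a power of 79.2" per cent. For a two-sided paired t test with n = 50, d = 0.4 and alpha 0.05, the noncentrality is 0.4 × √50 = 2.83 on 49 degrees of freedom, and the exact power is 79.18%. The figure reproduces, so the issue is one of design and not of arithmetic.

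**Baseline regressions.** No arithmetic applies. Set the marker list beside the confounder list: lipids, glucose, blood pressure, CRP and IL-6 are analysed, and no drug class that targets them is adjusted for.

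**Before-after tests.** Suppose chokeberry has no effect, and that k of 50 participants change a marker-relevant treatment, each shifting their own difference by s, in units of the SD of the paired difference. If all move the same way:

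spurious mean change = k × s / 50

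For example, 5 × 1 / 50 = 0.10 SD, and 5 × 2 / 50 = 0.20 SD, which is half of the plan's d = 0.4.

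The values of k, s and the direction are assumptions; the documents give none of them. Simulating the planned t test (40,000 trials per setting, normal differences, nominal 5%) gives these rejection rates:

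| Changers (of 50) | s = 0.5 | s = 1 | s = 1.5 | s = 2 |
|---|---|---|---|---|
| 1, same direction | 5.1% | 4.8% | 5.0% | 5.0% |
| 2, same direction | 5.2% | 5.4% | 5.6% | 6.4% |
| 3, same direction | 5.3% | 6.2% | 7.6% | 9.3% |
| 5, same direction | 6.0% | 9.2% | 13.5% | 18.5% |
| 8, same direction | 8.0% | 16.3% | 28.3% | 41.2% |

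With five changers in mixed directions and s from 1 to 2, a split of 4 against 1 gives about 5.9% to 7.3%. A split of 3 against 2 gives about 4.2% falling to 2.5–2.8% across repeated simulations. That is below nominal, because opposing shifts widen the SD while hardly moving the mean.

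The signed rank test is also inflated, but less: 12.0% and 13.8% for five aligned changers at 1.5 and 2 SD.

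**Does the remedy work?** Adding a medication-change indicator to a model for the change, or leaving out the changers, brings the rate back to about 5% in the settings simulated. Power at d = 0.4 after exclusion, by the same noncentral t formula, is:

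| Pairs left | 50 | 48 | 47 | 45 | 42 |
|---|---|---|---|---|---|
| Power | 79.2% | 77.5% | 76.6% | 74.7% | 71.6% |

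**The case against.** A reader might infer that the incomplete list is what lets a medication change pass as a chokeberry response. The documents do not support that link. The list belongs to the baseline regressions; it could name every drug and the paired test would be unchanged. The two points need separate remedies.

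A reader might also take the rates of 13% to 41% in the table as the likely size. They need 5 to 8 participants to change treatment relevant to the same marker within six weeks, all in the same direction, by 1.5 to 2 SD. Nothing in the documents supports this. Starts, stops and short courses can move a marker either way, and with one or two changers the effect is minor.

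Other objections stand in part:

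- In the regressions, a drug confounds the marker–methylation association only if it is also related to methylation. No size can be given for that part.
- The text available is the design and statistical material. Rules on stable medication, or on recording it, may exist elsewhere, so their absence from the study cannot be claimed. What can be said is that the analysis text does not use such information.
- Excluding people whose treatment changed conditions on an event after baseline, which the marker itself may have prompted. This can introduce selection, and is a good reason not to make the main conclusion depend on that analysis.
- Medication change is only one source of bias in an uncontrolled before-after design. It is, however, one that can be recorded and examined at little cost.

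**Conclusion.** The concern holds as two separate and modest points. First, the baseline confounder list omits the drug classes that act on the markers being analysed, and the comorbidity term is only a partial substitute. Second, the metabolic before-after tests, as written, count a between-visit change in marker-relevant treatment as part of the chokeberry response. The adjustments allowed elsewhere in the plan do not cover this.

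The second point ranges from negligible (about 5–6% false positives with 1–2 changers) to material (up to about 19% with five aligned changers), and mixed directions largely remove it. These figures assume 50 complete pairs, normal differences and no true effect. The case for acting rests on the low cost of the remedy, not on a demonstrated large bias.

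**What to change.** 1. **Baseline regressions.** In each model, add current use (yes/no) of the drug class that matches the marker: lipid-lowering, glucose-lowering, blood-pressure-lowering, or anti-inflammatory/steroid.
2. **Data.** Record these drugs at baseline and at week 6, so that a start, stop or change can be identified. If they are already collected, refer to that in the analysis text.
3. **Before-after tests.** Keep the planned paired test as the main analysis. For each metabolic endpoint, pre-specify one sensitivity analysis that leaves out participants whose marker-relevant treatment changed between visits, or a model for the change with a medication-change indicator. Report it beside the main result and consider it before the change is attributed to chokeberry. Do not require the two to agree formally: that would cost power and would make the conclusion depend on an event after baseline.

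**Cost.** A few more history items at two visits, one more term in each baseline model, and one extra analysis per endpoint. The sensitivity analysis has somewhat lower power (74.7% with 45 pairs against 79.2% with 50) and carries the selection risk noted above, which is why it should stay secondary. It needs no placebo or control arm and no change to anyone's treatment.

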### **Statistical Design and Power of Study**

All statistical analyses will use two-tail tests with the significance level set at 0.05, using version 9.4 of SAS software (SAS v9.4, Cary, NC). Statistical reports will emphasize our desire to characterize the evidence, in addition to reporting significance levels. Prior to final analyses, we will screen the data, consult with the overarching COBRE PI, project mentors and our COBRE admin core biostatistician as needed. Statistical assumptions will be tested, & appropriate data transformations or model adjustments will be used as needed. Our COBRE admin core biostatistician [name] has extensive experience with these methods and is equipped for supporting this study's needs.

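### Phase 2 chooses between the paired t test and Wilcoxon from the distribution of marker values rather than of paired differences, and names no effect estimate to accompany Wilcoxon

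*Combined protocol and SAP*

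**What the plan says.** All references are to the combined protocol and SAP.

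- **Phase 2 Specific Aim, distribution check.** A Kolmogorov–Smirnov "test will be applied to determine whether the continuous variables are normally distributed".
- **Phase 2 Specific Aim, choice of test.** The comparison with baseline has two branches. The first reads: "variables showing normal distributions will be evaluated using the paired t test". The second, for markers that fail the check, reads: "variables showing non-normal distributions will be evaluated using the Wilcoxon signed rank test". Neither branch refers to the change from baseline to six weeks.
- **Phase 2 Specific Aim, reporting.** "For the metabolic end points, the values will be expressed as means" with SD. No other summary, effect estimate or confidence interval is named for these endpoints.
- **Statistical Design and Power of Study.** Two general provisions apply: "appropriate data transformations or model adjustments will be used as needed", and "Statistical reports will emphasize our desire to characterize the evidence, in addition to reporting significance levels".
- **Phase 1 Specific Aim.** Log transformation and/or a non-parametric test is allowed for non-normal data, with results transformed back for interpretation. No scale is assigned to any metabolic marker.
- **Sample Size, Power and Attrition.** For 50 participants and an effect size of 0.4, "we have a power of 79.2% with a two-sided paired test". The scale of the 0.4 (raw or log) is not given. The section adds: "The median effect size from these studies in the literature (significant findings) is 1.12".

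**The concern.** A paired t test assumes that the within-person differences are roughly normal. It assumes nothing about the distribution of the marker at either visit. A marker can look normal at both visits and still have heavy-tailed changes, and a skewed marker can have nearly symmetric changes. A check on the values can therefore point to the less suitable test.

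The second problem is in reporting. Wilcoxon signed rank does not test the arithmetic mean change. If its p-value stands beside two arithmetic means, a reader may see a significant result next to a mean change whose own interval includes zero, with no estimate that matches the test. That sits poorly with the plan's stated aim of characterising the evidence as well as significance.

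**Working it through.** **Inputs from the plan:** 50 pairs, effect size 0.4, two-sided 0.05, stated power 79.2%.

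**Assumed, because the plan gives none:** the distribution of each marker, the log-SD (0.3 to 1.0), the visit correlation (0.6; range 0.4 to 0.8) and 50 complete pairs. Simulations used a Lilliefors-corrected Kolmogorov–Smirnov check at 5% (critical D 0.1245), with 20,000 trials per cell at effect 0.4.

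**1. The plan's own figure.** The noncentrality is 0.4 × √50 = 2.828 on 49 df, and the two-sided critical value is 2.010. Power = P(|T| > 2.010) = 0.7918. The stated 79.2% reproduces exactly.

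**2. Does it matter what is checked?** Yes.
- Lognormal marker, log-SD 0.5: normality is rejected in 70–73% of trials for values at a single visit, but in 36–40% for the differences.
- Normal marker with t(3) change: checking values and checking differences lead to different tests in 43–49% of trials.

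**3. Cost in power.** Normal marker, t(3) change, effect 0.4 SD of the change:
- rule as written: 0.851 (baseline values checked) or 0.861 (either visit checked);
- check on differences: 0.934, a gain of 0.934 − 0.861 = 0.073 to 0.934 − 0.851 = 0.083.

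**4. Agreement of test and reported mean.** Lognormal marker, correlation 0.6, effect 0.4 SD of the log differences. Among results significant under the rule (either visit checked), the share whose raw mean-change 95% CI includes zero is 8.1%, 19.2% and 29.0% at log-SD 0.5, 0.8 and 1.0.

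**5. Type I error.** The rule gives 0.048 to 0.054 in the null runs.

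**6. Is the planned power affected by skewness?** That depends on the scale of the 0.4.

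| Log-SD | 0.4 on log differences: rule (correlation 0.6) | 0.4 on log differences: log paired t (correlation 0.6) | 0.4 on raw differences: Wilcoxon (correlation 0.3–0.8) |
|---|---|---|---|
| 0.3 | 76% | 79% | 79–80% |
| 0.5 | 73–74% | 79% | 83–84% |
| 0.8 | 71–72% | 79% | 92–95% |
| 1.0 | 70% | 79% | 98–99% |

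The two definitions are different effects. With log-SD σ and correlation ρ, the log shift is δ = 0.4σ√(2(1−ρ)). At σ = 0.5 and ρ = 0.6, δ = 0.4 × 0.5 × 0.894 = 0.179. The raw mean fall is e^(σ²/2)(1 − e^(−δ)) = 1.133 × 0.164 = 0.186. The raw variance of the difference is e^(σ²)[(e^(σ²) − 1)(1 + e^(−2δ)) − 2e^(−δ)(e^(ρσ²) − 1)] = 0.272, so its SD is 0.522. The raw standardised effect is then 0.186 / 0.522 = 0.36. At log-SD 0.8 and 1.0 it is 0.30 and 0.25.

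**7. Would checking differences restore the log-scale loss?** No. With raw differences checked, power is 0.730, 0.705 and 0.700 at log-SD 0.5, 0.8 and 1.0, against 0.742, 0.715 and 0.703 under the rule. Only a change of scale moves it, and that can work the other way. If change is additive on the raw scale, the rule gives 77–78% and Wilcoxon on logs gives 68–73%.

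**The case against.** **The general provisions may cover this.** The Statistical Design section says that assumptions will be tested and allows transformation. Testing the paired t assumption properly means looking at differences, and the word variables could be read as change scores. This stands in part: transformation is permitted, so the missing scale is an open choice rather than an omission. But the specific rule in Phase 2 is the one an analyst would program, and it names the variables and not their changes.

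**Means with SD may be only a descriptive convention.** That is fair, and the plan does not forbid other estimates. It still names none for Wilcoxon.

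**The study is exploratory, and effects may be large.** In the lognormal runs, power under the rule is at least 99.8% at an effect of 0.8 and essentially 100% at 1.12. That limits the power cost. However, the plan says the 1.12 comes from significant findings, and its own planning value is 0.4.

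**A tempting stronger reading is that true power is about 70–74% and the 79.2% is wrong.** The documents do not support this. The 79.2% is exact for its inputs, lognormality alone does not lower it, and the lower figures need 0.4 to be a log-scale effect, which the plan does not say. Nor is that loss caused by checking values instead of differences, as step 7 shows.

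**Conclusion.** The point holds as a defect in the stated rule for choosing the test and in the estimate reported with it. It is not an error in the power calculation and not a threat to validity.

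- **Choice of test:** about 85% power under the rule against about 93% with differences checked, in the heavy-tailed example (normal marker, t(3) change, 50 pairs, effect 0.4). This illustrates what can happen and does not predict the result for any named marker.
- **Mismatched estimate:** 8–29% of significant results, under the lognormal model with log-SD 0.5 to 1.0, log-scale effect 0.4 and correlation 0.6.
- **Conditional power statement:** only if the 0.4 is a log-scale effect with proportional change is power under the rule about 70–75% (log-SD 0.5 to 1.0), against about 79% for a paired t test on logs. If 0.4 is the standardised raw difference, power is 79% or more.

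A reader might also infer that the skewed markers ought to be logged. The documents give no log-SD, correlation or pattern of change for any marker, so that cannot be settled from them.

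**What to change.** In the Phase 2 Specific Aim section:

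1. Base the distribution check, and the choice of test, on the paired differences (week 6 minus baseline) on the analysis scale, not on the marker values.
2. Report with each test its matching estimate and 95% CI: the mean difference for the paired t test and the Hodges-Lehmann estimate for Wilcoxon. If a marker is analysed on logs, transform the estimate back to a ratio. Means with SD can stay as description.
3. Optional: where a marker is expected to change in proportion to its level, fix the log scale before week-6 data are analysed. This is a trade-off, because logs lose power if change is additive. It also needs a rule for zero or below-detection values.

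The cost is a few sentences in the SAP, a small amount of programming and, for some markers, a reported summary other than the mean change. No extra data or participants are needed.
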